#### **3.1.2       Adverse events of special interest (AESIs)**

An AESI is an AE of scientific and medical interest specific to the understanding of the investigational product (IP), nirsevimab and may require close monitoring and rapid communication by the Investigator to the Sponsor. An AESI may be serious or nonserious. Adverse events of special interest are defined as AEs of immediate (type I) hypersensitivity (including anaphylaxis), thrombocytopenia, and immune complex disease (eg, vasculitis, endocarditis, neuritis, glomerulonephritis, serum sickness, and arthralgias) following the administration of nirsevimab.

### **3.1.3 Skin reactions and skin hypersensitivity reactions**

All skin reactions and skin reactions identified as hypersensitivity/allergic reactions and the incidence and relationship to IP will be summarized by SOC and PT. It will be done for any post-dosing skin or skin hypersensitivity reactions through Day 361 to assist in determination of the etiology of the reaction. Information will be collected regardless of event severity, duration, time of onset post dosing, or relationship to IP.

### **3.1.4 New onset chronic disease (NOCD)**

An NOCD is a newly diagnosed medical condition that is of a chronic, ongoing nature. It is observed after receiving nirsevimab and is assessed by the Investigator as medically significant. Examples of NOCDs include, but are not limited to diabetes, autoimmune disease (eg, lupus, rheumatoid arthritis), and neurological disease (eg, epilepsy).

## **3.2 Secondary variables**

### **3.2.1 Pharmacokinetic (PK) variables**

The PK variable is nirsevimab serum concentration.

### **3.2.2 Anti-drug antibodies (ADA) variable**

The ADA variable is the incidence of ADA to nirsevimab in serum. The impact of ADA on PK, and the association with TEAEs and TESAEs, will be assessed, if data permit.

### **3.2.3 Efficacy variables**

The efficacy variables are the incidence of protocol-defined medically attended lower respiratory tract infections (LRTI) (inpatient and outpatient) due to reverse transcriptase-polymerase chain reaction (RT-PCR)-confirmed RSV, also described as the medically attended RSV LRTI, and the incidence of protocol-defined hospitalizations due to RT-PCR-confirmed RSV, also described as RSV LRTI hospitalization, through 150 days post dose, after 150 days post dose, and through 360 days post dose. For subjects with multiple medically attended RSV LRTI events (inpatient or outpatient) or multiple RSV LRTI hospitalizations, only the first occurrence will be used in the analysis, unless stated otherwise.

[figure not shown]
The determination of medically attended RSV LRTI will be based on objective clinical LRTI criteria (described in Section 4.3.1.1 of the CSP and in [Appendix 1](#) of this SAP) and RSV central laboratory test results. Protocol-defined medically attended LRTI will be identified when at least one item of “Physical exam findings” and at least one item of “Clinical signs of severe disease” from ‘Respiratory Illness Assessment’ eCRF page are selected as ‘yes’. If there are multiple assessment settings associated with the same event, then assessment data of those visits will be combined to determine whether the event meets criteria for the protocol-defined medically attended RSV LRTI.

Testing for RSV will be performed centrally using a United States Food and Drug Administration (US FDA)-cleared and Conformité Européenne or European Conformity marked in vitro diagnostic real-time RT-PCR assay. The RSV test results obtained from analyzing the respiratory secretions using a validated RSV RT-PCR assay for the detection of RSV A or RSV B are performed in a central laboratory. Respiratory syncytial virus tests are also performed by local laboratories, if available, and the test results are captured in the ‘Respiratory Illness Assessment’ eCRF page.

The events of “RSV LRTI hospitalization” are a subset of “medically attended RSV LRTI,” which are determined based on objective clinical LRTI criteria (described in Section 4.3.1.1 of the CSP and in [Appendix 1](#) of this SAP) and RSV test results obtained from central laboratory using a validated RSV RT-PCR assay for the detection of RSV A or RSV B. If any of the settings associated with the medically attended RSV LRTI is hospitalization, then this medically attended RSV LRTI will be counted as RSV LRTI hospitalization.

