2.2 Secondary Objectives and Associated Endpoints

The secondary objectives and associated endpoints are described in [Table 2](#).

Table 2 Secondary Objectives and Associated Endpoints

Type	Objective	Endpoint
PK	To evaluate the PK of nirsevimab	Summary of nirsevimab serum concentrations
ADA	To evaluate ADA responses to nirsevimab in serum	Incidence of ADA to nirsevimab in serum
Efficacy	To assess the efficacy of nirsevimab when administered as a single IM dose to infants \leq 24 months of age	Incidence of medically attended LRTI (inpatient and outpatient) and hospitalizations due to RT-PCR-confirmed RSV through 150 days after administration of nirsevimab

ADA = antidrug antibody; IM = intramuscular; LRTI = lower respiratory tract infection; PK = pharmacokinetics; RSV = respiratory syncytial virus; RT-PCR = reverse transcriptase-polymerase chain reaction.

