3.2.3 Rationale for Endpoints

Nirsevimab is being developed to provide RSV immunoprophylaxis for all infants and young children, including immunocompromised children ≤ 24 months of age. The primary endpoint for this study is safety and tolerability. The standard measures of TEAEs/TESAEs, AESIs, and NOCDs will be used for this assessment. All subjects will be followed for approximately 1 year after dosing with nirsevimab.

Serum concentrations of nirsevimab at selected time points will be evaluated as a secondary endpoint to confirm that serum concentrations are maintained at an efficacious level for at least 5 months after dosing. PK data will be summarized by descriptive statistics. PK data obtained in this study will be compared to the PK data from the Phase 2b, Phase 3, and the Phase 2/3 studies. For infants and children who require hospitalization for LRTI or any respiratory infection, an additional serum sample for measurement of nirsevimab concentration and ADA will be obtained contemporaneous with time of hospitalization.

To determine nirsevimab serum levels post dosing and to correlate with the potential development of ADA, serum concentrations will be measured up to 360 days post dose. ADA to nirsevimab will be measured at selected time points throughout the study and up to 360 days post dose.

This study will also summarize efficacy of nirsevimab in terms of incidence of RSV LRTI. RSV results in a significant burden of disease consisting of hospitalization, visits to the ER, and visits to outpatient clinics. This endpoint is designed to allow the capture of this total burden of disease. A separate endpoint of RSV hospitalization will also be evaluated.

Exploratory endpoints will examine CCI [REDACTED]

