RSV	*Lower Respiratory Tract	*Medical Significance
RSV Confirmed: 
Positive by central laboratory RT-PCR assay	Documented PE findings localizing to lower respiratory tract: 
RhonchiRalesCracklesWheeze	Objective measures of clinical severity: 
Increased respiratory rateHypoxemiaAcute hypoxic or ventilatory failureNew onset apneaNasal flaringRetractionsGruntingDehydration due to respiratory distress

LRTI = lower respiratory tract infection; PE = physical examination; RSV = respiratory syncytial virus; RT-PCR = reverse transcriptase-polymerase chain reaction.

*Note: One item from each column is required to meet the protocol-defined endpoint of RSV LRTI.

RSV Hospitalization

An RSV hospitalization is defined as either (1) a respiratory hospitalization with a positive RSV test within approximately 2 days of hospital admission (primary) or (2) a new onset of respiratory symptoms in an already hospitalized subject, with an objective measure of worsening respiratory status and positive RSV test (nosocomial). Primary and nosocomial RSV hospitalization are further defined below.

Primary RSV Hospitalization

RSV diagnostic testing will be performed on respiratory secretions obtained within approximately 2 days before or after admission for subjects hospitalized for respiratory infection (upper or lower respiratory tract). If the RSV diagnostic test (performed centrally via RT-PCR) is positive, the hospitalization will be classified as a primary RSV hospitalization. Deaths that can be demonstrated as caused by RSV (by autopsy or clinical history and virologic evidence) will also be considered as primary RSV hospitalization endpoints.

Nosocomial RSV Hospitalization

Subjects hospitalized for a respiratory illness or non-respiratory illness whose RSV diagnostic test is negative may develop nosocomial RSV illness during the study.

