If signs (such as retractions, rhonchi, wheezing, crackles, or rales) of a new lower respiratory illness occur during a hospitalization, whatever the reason for hospitalization, and there is an objective measure of worsening respiratory status (that is, new requirement for supplemental oxygen, increase in supplemental oxygen requirement from prior to the onset of symptoms, or need for new or additional mechanical ventilation), a specimen will be collected within approximately 2 days from worsening of respiratory status for RSV diagnostic testing by the

central laboratory. For any subject who is hospitalized for a respiratory infection (upper or lower respiratory tract), the subject must return to his/her baseline respiratory status or be clearly resolving the preceding respiratory illness before a subsequent respiratory deterioration for a nosocomial RSV hospitalization event can be determined.

If the RSV diagnostic test (performed centrally via RT-PCR) is positive, the subsequent hospital days will count as a nosocomial RSV hospitalization. The days of RSV hospitalization will be counted beginning with the start of the respiratory deterioration that resulted in the RSV diagnostic test.

RSV LRTI Outpatient Events

Subjects who seek outpatient medical attention, including ER and urgent care visits, for an LRTI should have respiratory secretions obtained within approximately 2 days after the initial healthcare provider assessment.

[figure not shown]
Respiratory Secretions for RSV Detection

Respiratory secretions for RSV testing must be collected from all subjects with LRTIs (inpatient or outpatient) and from all hospitalized subjects with any new respiratory infection (upper or lower) within approximately 2 days after the initial healthcare provider assessment and diagnosis. Nasal secretions will be obtained unless the subject is intubated, and then tracheal secretions may be obtained.

[figure not shown]
Respiratory secretions will be tested in a central laboratory for RSV using the US FDA-cleared and Conformité Européenne or European Conformity-marked in vitro diagnostic real-time RT-PCR assay (Lyra RSV + hMPV assay; Quidel Corporation, San Diego, CA). Testing may include other respiratory pathogens.

The respiratory samples will be retained at AstraZeneca or designee for a maximum of 15 years following the issue of the CSR to properly address potential questions from regulatory authorities.

CC1

CCI

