#### **Analysis of Incidence of RSV hospitalization**

The events of “RSV hospitalization” are a subset of “medically attended RSV LRTI,” and RSV test results are obtained from central laboratory. In addition, deaths that can be

demonstrated as caused by RSV (by autopsy or clinical history and virologic evidence) will also be considered as medically attended RSV hospitalization events.

The incidence of RSV hospitalization through 150 days after dosing will be summarized. For subjects with multiple RSV LRTI hospitalizations, only the first occurrence will be used in the analysis. RSV LRTI hospitalization will also be summarized by RSV subtype (RSV A or RSV B). This summary will be based on observed events and data summary will be presented through 150 days post dose, after 150 days post dose and through 360 days post dose.

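### The SAP labels its RSV hospitalization endpoint 'protocol-defined' but derives it as the inpatient subset of protocol-defined RSV LRTI (plus RSV deaths), which is not the protocol's definition and is not declared in SAP Section 6

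*SAP*

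**What the plan says.** **Protocol.** The secondary efficacy endpoint in Section 2.2 (Table 2) has two parts: medically attended RSV LRTI and "hospitalizations due to RT-PCR-confirmed RSV through 150 days after administration of nirsevimab". Section 3.2.3 treats the second part as distinct: "A separate endpoint of RSV hospitalization will also be evaluated". Section 4.3.1.1 then defines it under its own heading, with two limbs.

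- *Primary.* The subject is admitted for a respiratory infection of either the upper or the lower tract, and secretions are sampled within about 2 days before or after admission. "If the RSV diagnostic test (performed centrally via RT-PCR) is positive, the hospitalization will be classified as a primary RSV hospitalization". Deaths shown to be caused by RSV also count.
- *Nosocomial.* The starting condition is "If signs (such as retractions, rhonchi, wheezing, crackles, or rales) of a new lower respiratory illness occur during a hospitalization". It also requires a new or increased need for oxygen or ventilation and a positive central RT-PCR.

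**SAP.** Section 3.2.3 names the variable as the "incidence of protocol-defined hospitalizations due to RT-PCR-confirmed RSV, also described as RSV LRTI hospitalization", and Section 4.2.5.3 uses the label 'protocol-defined' again. The derivation is different. Both sections make the endpoint a subset of medically attended RSV LRTI. That event requires a positive central RT-PCR, at least one of rhonchi, rales, crackles or wheeze, and at least one severity sign (Appendix 1). Such an event becomes a hospitalization "If any of the settings associated with the medically attended RSV LRTI is hospitalization". Table 1 repeats this for the secondary endpoint, with setting of care given as inpatient. Section 4.2.5.3 adds RSV-caused deaths.

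SAP Section 1 undertakes to describe every change from the protocol in Section 6. Section 6 lists two: the unplanned interim analysis and the PK summary rules.

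**The concern.** The two documents give one name to two different sets of events. The protocol's primary limb needs only a respiratory admission and a positive test. The SAP adds a chest finding and a severity sign. A child admitted with an RSV-positive upper respiratory infection is a secondary-endpoint event under the protocol and not under the SAP.

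Efficacy in this uncontrolled study is purely descriptive, so the reported incidence is the entire result for this endpoint. A reader who sees the label would take the figure for the protocol's endpoint and would find nothing in Section 6 to correct that.

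**Working it through.** The plan gives no figure to reproduce here. The check compares definitions and then works out what one reclassified subject does to the result.

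**Step 1: run event types through both rules** (Protocol 4.3.1.1; SAP 3.2.3, 4.2.5.3 and Appendix 1).

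| Event | Protocol | SAP |
|---|---|---|
| Respiratory admission, RT-PCR positive in the sampling window, chest finding and severity sign both present | counted | counted |
| Admission for upper-tract infection, RT-PCR positive, LRTI criteria not met | counted | not counted |
| Admission for lower-tract infection, RT-PCR positive, chest finding or severity sign missing | counted | not counted |
| Inpatient with new retractions and new oxygen need but none of the four chest findings, RT-PCR positive | counted (nosocomial) | not counted |
| RSV LRTI arising in an inpatient without new or increased oxygen or ventilation need | not counted | counted |
| RSV LRTI sampled as an outpatient, admitted more than about 2 days later | not counted as primary | counted |
| Death shown to be caused by RSV | counted | counted |

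Row 4 arises because retractions are a qualifying sign for the protocol's nosocomial limb, while SAP Appendix 1 lists them only in the severity column.

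**Step 2: direction.** For admissions sampled in the protocol's window, the SAP rule can only remove events. For nosocomial events, and for outpatient illness admitted late, it can also add them. The net direction is therefore not certain.

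**Step 3: can the protocol's count be recovered elsewhere in the SAP?** Section 4.2.5.3 (Other efficacy analyses) summarizes and lists hospitalization for any respiratory illness, so the events stay visible. In that summary each subject appears once, with events ranked LRTI over non-LRTI first and RSV over non-RSV second. A child with one non-RSV LRTI admission and one RSV-positive upper-tract admission would appear as non-RSV LRTI. The summary therefore need not equal the protocol's count. SAP 4.2.6.4 uses the deterioration date, but only for length of stay. Four rows of Table 1 are redacted and may cover more, but the text calls them exploratory.

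**Step 4: effect of one subject.** Inputs: about 100 subjects in total (Protocol 4.1.1, SAP 1.3), about 50 in each dose group (Protocol 3.1.2), and presentation by dose group (SAP 4.1).

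- Overall: 1/100 = 1.0 percentage point. Per group: 1/50 = 2.0 points.
- The exact (Clopper-Pearson) 95% upper limit for 0/n is 1 − 0.025^(1/n). For n = 100 it is 3.62%; for n = 50 it is 7.11%.
- For 1/n, the lower limit is 1 − 0.975^(1/n), and the upper limit solves (1−p)^n + n·p·(1−p)^(n−1) = 0.025. For 1/100 the interval is 0.03% to 5.45%; for 1/50 it is 0.05% to 10.65%.

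Moving from no event to one thus raises the upper limit from 3.62% to 5.45% overall, and from 7.11% to 10.65% within a group.

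**Step 5: a related ambiguity.** For both secondary endpoints, SAP Table 1 shows LRTI in the column for the investigator's assessment. SAP 3.2.3, SAP Appendix 1 and Protocol Table 6 contain no such condition. It is unclear whether a programmer should apply it.

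**The case against.** The best defence is that the SAP states the narrower rule openly. It gives the alternative name, uses the word subset and sets out a separate row in Table 1. On this view, what is missing is one line in Section 6 and a corrected label. That is fair as to intent, but the rule as written would still produce an incidence that is not the protocol's.

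A second argument is that the narrower endpoint is useful. Protocol 1.4.3 reports the Phase 2b result as RSV LRTI hospitalization, and efficacy is to be extrapolated from that study. This is a good reason to keep the endpoint under its own name, or to declare it as the secondary one. It does not justify the present label.

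Third, the excluded events are listed, and the example of one child with two different admissions is narrow. That stands as mitigation, but a listing and possible exploratory rows do not restore the secondary endpoint.

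Fourth, Protocol 3.1.1 and 4.3.1.1 mention a clinical assessment of LRTI, which the Table 1 column may simply reflect. However, both sections present the objective definition as additional to that assessment, so the question remains open.

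Two cautions on scale are right. The SAP's efficacy section plans summaries and no confidence intervals, so the intervals above only illustrate precision. The figure of about 50 per group comes from the protocol's split by RSV season, whereas SAP 1.2 assigns dose by age and weight and gives no group sizes in its text.

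**Conclusion.** The concern holds. The SAP's hospitalization endpoint is not the one defined in Protocol 4.3.1.1, it carries a label saying that it is, and Section 6 does not declare the change. Its size can be given only per subject: 1.0 percentage point overall if about 100 are dosed, and 2.0 points within a group if each has about 50. No relative under- or overstatement can be given, because the documents report no RSV hospitalization rate for this population.

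The conclusion rests on the global protocol and the SAP text that is not redacted. The Japan amendment that the SAP also cites was not available. The primary safety endpoint and the sample size are unaffected. This should be fixed, but it does not undermine the study.

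**What to change.** - In SAP 3.2.3 and 4.2.5.3, derive RSV hospitalization through 150 days post dose by the primary and nosocomial definitions of Protocol 4.3.1.1. RSV-caused deaths are already included.
- Report RSV LRTI hospitalization as an additional, separately named endpoint.
- If the narrower endpoint is meant to be the secondary one, declare and justify that in Section 6, remove the 'protocol-defined' label from it, and report both.
- State whether the investigator-assessment column of Table 1 is a condition for the two secondary endpoints, and bring it into line with SAP 3.2.3, Appendix 1 and Protocol Table 6.

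The cost is SAP wording, a derived flag and a summary row, repeated across the planned presentations. Protocol 3.1.1 already requires samples and assessment forms for every respiratory hospitalization. The nosocomial limb needs somewhat more programming. It depends on the change in oxygen or ventilation need and, after an earlier respiratory illness, on return to baseline or clear resolution. The documents do not show whether that resolution status is captured as a field, so some events may need case review. The reported incidence may turn out less favourable.

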### 3.3 Exploratory variables

CCI

A large rectangular area of the page is completely blacked out, indicating that the content has been redacted. The word 'CCI' is printed in red at the top left corner of this redacted area.

#### 3.3.4 Healthcare resource utilization (HRU)

The magnitude of HRU will be measured by:

- the number of admissions to hospitals and duration of stay;
- the number of admissions to the intensive care units (ICUs) and duration of stay;
- the number of subjects who require respiratory support (using Continuous Positive Airway Pressure [CPAP] or mechanical ventilation) and duration of use, and the number of subjects requiring supplemental oxygen and duration of use;
- number and type of outpatient visits, eg, outpatient emergency department (ED), urgent care, outpatient clinic;
- the number of pre-specified over-the-counter (OTC) medications (analgesics/antipyretics) use;
- the number of pre-specified prescription medication (systemic antibacterial agents) use;

- the number of anti-wheezing medication use.

## 4 ANALYSIS METHODS

All analyses described will be conducted on the as-treated population and as-treated Japan subpopulation as defined in Section 2.1 unless stated otherwise.

No formal statistical comparisons are planned.

### 4.1 General principles

There are 2 planned analyses for this study: an interim analysis and a final analysis. The interim analysis will be conducted when subjects enrolled globally by the end of 2021 have been followed through Day 151. The final analysis will be conducted when all subjects have completed the last visit of the study (Day 361). The data will be validated as defined in the Data Management Plan.

- For the visit-based summaries for PK/ADA, CCI and clinical laboratory data, the summaries will be based on the scheduled visits using adjusted analysis-defined visit windows. The adjusted analysis-defined windows will be based on the collection schedule listed in the CSP and summaries will be windowed to the closest scheduled visit for those data. Visit windows have been constructed so that every observation collected can be allocated to a particular visit. All data will be included in the listings. If multiple readings are recorded within a single analysis-defined visit window, the following rules will apply: If there are 2 or more valid, non-missing observations within the same visit window, and
  - if they are on different days, then the non-missing one which is closest to the scheduled visit day will be used in the analysis.
  - if they are on the same day which is closest to the scheduled visit day, then the non-missing one with the later collection time will be used in the analysis.
- If 2 or more valid observations are equidistant from the scheduled visit, and
  - if they are on different days, then the non-missing post-dose observation with the earlier collection date will be used in the analysis for the post-baseline observations, and the non-missing pre-dose observation with the later collection date will be used in the analysis for the screening observations.
  - if they are on the same day, then the non-missing observation with the later collection time will be used in the analysis.
- For LRTI visits or unscheduled visits, if 2 or more valid observations are collected on the same day, then the non-missing observation with the later collection time will be included in the analysis.
- If a visit window does not contain any observations, then the data will remain missing.
- For the visit-based summaries for ADA, if both ADA positive and negative samples are available within a subject's visit, ADA positive will be reported.

- For summary Statistics of PK data following rules apply:
  - Handling of samples below LLOQ, samples should be imputed to the LLOQ (0.5 µg/mL)
  - Summary statistics should not be presented in case of  $\geq 50\%$  of samples  $< \text{LLOQ}$  (see specific details of reporting in Section 4.1.7)

For assignment of data to adjusted analysis-defined visit windows, study day will be defined as defined in Section 4.1.3.

The adjusted analysis-defined windows for PK/ADA, CCI are defined in [Appendix 2](#), and for clinical laboratory data are defined in [Appendix 3](#).

Data will be summarized for the overall study population, as well as for Japan only. Data will also be presented by the actual dose administered; ‘nirsevimab 50mg/100mg’, ‘nirsevimab 200mg’ and ‘total’, unless stated otherwise.

Data analyses will be performed by IQVIA under the direction of AstraZeneca using the SAS® System Version 9.4 or higher (SAS Institute Inc., Cary, NC) in a SAS GRID environment.

